6.5.12.9 Severity assessment

The investigator will use the adjectives MILD, MODERATE, or SEVERE to describe the maximum severity of the AE. For the purpose of consistency, these severity grades are defined as follows:

MILD	Does not interfere with patient's usual function
MODERATE	Interferes to some extent with patient's usual function
SEVERE	Interferes significantly with patient's usual function

6.5.12.9.1 Severity versus seriousness

A mild, moderate, or severe AE may or may not be serious, see section 6.5.12.4. These terms are used to describe the intensity of a specific event. Medical judgement should be used on a case-by-case basis.

For example, a headache may be severe in intensity, but would not be classified as serious unless it met one of the criteria for serious events listed above.

6.5.12.10 Causality assessment

For each AE, the investigator must make a causality assessment to determine if there is a reasonable possibility that the study treatment caused the AE. The AE is assessed as related or not related to the study treatment.

Sobi

Eftrenonacog alfa/Alprolix® - Efmorocog alfa/Elocta®

Clinical Study No: Sobi.HAEM89-007

6.5.12.11 Adverse events of special interest

The following are considered adverse events of special interest:

- inhibitor development
- thrombotic events
- serious hypersensitivity reaction including anaphylactic reactions

6.5.12.12 Serious adverse event reporting

Both serious and non-serious AEs are to be reported on the AE page of the eCRF as specified in the eCRF instructions.

If an SAEs occurs, Sobi Good Pharmacovigilence Practice (GVP) will be notified by e-mail to [contact] by the investigator entering the required information about the SAE into the appropriate module of the eCRF using the designated SAE form within 24 hours of awareness of the event by the investigator. This is also applicable for SAE follow-up information.

All SAEs must be recorded on the eCRF SAE form, irrespective of the study treatment received by the patient, and whether or not this event is considered by the investigator to be related to study treatment. The investigator must complete the eCRF SAE form in English and must assess the causal relationship of the event to study treatment.

The eCRF SAE collection form is not the same as the AE eCRF form. The forms must be completed in a consistent manner. For example, the same AE term should be used on both forms.

If the eCRF is not functioning, the SAE can be reported by emailing a completed paper SAE report form, using the e-mail address [contact]. The event must be updated electronically in the eCRF by the clinical site once eCRF function resumes.

All new information obtained, relevant to an SAE report, should be forwarded to Sobi GVP by e-mail to [contact] within the same timeframe as the initial information.

The investigator shall provide Sobi GVP with sufficient information to enable a complete medical assessment of the reported event. Best efforts shall be made by the investigator to provide Sobi with additional information related to any SAE as requested.

An investigator who receives an investigator safety report describing an SAE or other specific safety information (e.g., summary or listing of SAEs) from Sobi/CRO, will review it and will notify the IECs, if appropriate according to local requirements.

Sobi Global pharmacovigilance & patient safety (GPV) will report SUSARs to the relevant Health Authorities in all concerned countries according to local regulations. Sobi/CRO will notify central IECs according to local requirements, and investigators.

6.5.12.13 Follow-up of unresolved adverse events

All reported AEs should be followed up until they are resolved or the investigator assesses them as chronic or stable, or the patient's participation in the study ends, i.e., until the last scheduled

Confidential

Page 38 of 56

Sobi

Eftrenonacog alfa/Alprolix® - Efmorocog alfa/Elocta®

Clinical Study No: Sobi.HAEM89-007

visit. How to report changes in an ongoing AE during a patient's participation in the study is described in the eCRF instructions.

In addition, all serious and non-serious AEs assessed by the investigator as related to the study treatment should continue to be followed up until they resolve or until the investigator assesses them as "chronic" or "stable", even after the patient's participation in the study is over, but without further recordings into the eCRF.

6.5.12.14 Exposure during pregnancy and breastfeeding

All events of exposure to the study treatment during pregnancy (female patient or male patient's partner) or breastfeeding, shall be reported to Sobi GPV by e-mail to [contact] within 24 hours of awareness by any study personnel using the Pregnancy Notification Form, whether the exposure is associated with an AE or not. This includes all situations where a female is or has been found to be pregnant after being exposed to study treatment; directly, indirectly or via her partner (paternal exposure).

In all reported situations of exposure during pregnancy, Sobi will provide the investigator with a Pregnancy Report Form which shall be completed and returned by the investigator. The investigator is responsible for monitoring the outcome of the pregnancy and to inform Sobi of relevant information and any information requested related to the outcome of the pregnancy.

Before collecting any details on the pregnancy, its outcome, the birth, and health of the baby, a separate consent form should be collected from the mother and/or the father of the child, as required by local regulations.

Any AEs and SAEs observed during and in relation to pregnancy, delivery or breastfeeding should be recorded in the eCRF and, as applicable, be reported to Sobi as described previously in this section.

6.5.12.15 Appropriateness of safety measurements

The safety measurements in this study is in line with the scope and type of the clinical study, the level of knowledge on the safety profile of the study drugs, the disease profile of the study patients, and supported by EU regulatory requirements.

7 Quality control and quality assurance

This study will be conducted in compliance with this protocol, study specific procedures, Sobi and/or CRO SOPs, the ICH GCP Guideline (2), and applicable regulatory requirements.

The sponsor will systematically review the study quality management to identify, evaluate and control risks to study critical processes and data which would affect patient safety and reliability of study data.

The Sponsor will establish a systematic, prioritized, risk-based approach to monitoring and has chosen a combination of on-site and centralized monitoring.

Sobi

Eftrenonacog alfa/Alprolix® - Efmorocog alfa/Elocta®

Clinical Study No: Sobi.HAEM89-007

Monitoring visits to the study site will be performed periodically during the study, to help ensure compliance with the protocol, study specific procedures and applicable regulatory requirements. Source documents will be reviewed for verification of agreement with data in CRFs. All patient informed consent forms will be reviewed. The investigator or institution guarantees access to source documents by Sobi, its representatives, and appropriate regulatory agencies.

The study site may be patient to a quality assurance audit by Sobi or its representatives, as well as inspection by appropriate regulatory agencies.

It is important that the investigator(s) and the(ir) relevant personnel are available during the monitoring visits and possible audits and that sufficient time is devoted to the process.

8 Statistical plan

8.1 Determination of sample size

With a sample size of 250 patients (200 with haemophilia A and 50 with haemophilia B) assuming a standard deviation of 13, the mean change from baseline in Total HEAD-US score will be estimated with a level of accuracy that is lower than a clinically meaningful worsening of 2, e.g. a half width of 1.61 (Table 3). The standard deviation is based on the expected variability among the patients with regards to prior treatment before enrolment and the diversity of joint status.

Table 3 **Determination of sample size**

Confidence level	Standard deviation	n	Half width
95%	7	250	0.87
95%	10	250	1.25
95%	13	250	1.61
95%	13	200	1.80

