Favourable joint outcomes are expected with modern haemophilia A and haemophilia B management. However, evaluation of long-term treatment outcomes is hampered by the delay between bleeding episodes during childhood and resulting joint outcomes in adulthood. Future research with combined US and/or Magnetic resonance imaging (MRI) is needed to better understand joint outcomes. Ultrasound paired with physical examination increases the sensitivity for detection of joint damage (23). Accordingly, the expected joint health outcomes, based on HEAD-US scoring, in patients receiving adequate prophylactic treatment is at least the maintenance of a stable joint status or the improvement in reversible lesions for the patients with already established joint damage.

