6.1 Overall study design and plan

This is a prospective, low-interventional, single-arm, multicentre study to describe the joint health over an 18-month period of prophylactic treatment with rFVIIIFc or rFIXFc in patients with haemophilia A or haemophilia B in a real-world setting. Approximately 250 patients will be enrolled in the study. Around 80% of the patients are expected to have haemophilia A and around 20% haemophilia B.

Retrospective data from patient medical records will be collected for at least 6 months before enrolment in the study. From enrolment and throughout the study, patients will perform on-site study visits at 6-month intervals. Each patient is expected to actively participate in the study for 18 months (from baseline to end of study [EOS] visit).

Joint health will be assessed with HEAD-US and HJHS scoring. Quality of life and physical activity will be assessed with PROs. Patients will be on prophylactic treatment with rFVIIIFc or rFIXFc according to usual clinical practice and the dosing guide in the respective Summary of Product Characteristics (SmPC). Choice of treatment will not be dictated by the study protocol.

The recruitment period is planned to be approximately 12 months from the timepoint when the first patient is enrolled in the study. Around 60 sites in approximately 11 European countries are expected to participate in the study.

No specific evaluation committees will be utilized for this study, since it is a low-interventional study having no interventions posing more than minimal risk to the patients.

Interim analyses are planned to be performed during the study. The first interim analysis is to be performed once recruitment is completed. The purpose of the first interim analysis is to assess the baseline variability of HEAD-US score results and to share baseline characteristics with the haemophilia community. The second interim analysis is planned to be performed once at least 50% of the patients have completed their 12-month visit and will evaluate the joint health status at that time.

In an optional, exploratory sub-study, data will be collected via the florio HAEMO app. All exploratory endpoints and objectives in the study are related to the exploratory sub-study.

[figure not shown]
The overall study design is described in Figure 1.

Sobi

Eftrenonacog alfa/Alprolix® - Efmorocog alfa/Elocta®

Clinical Study No: Sobi.HAEM89-007

Figure 1 Study Design

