6.2 Discussion of study design, including the choice of control groups

This prospective, low-interventional, multicentre study is being conducted to describe the joint health over an 18-month period in patients on prophylactic treatment with rFVIIIFc or rFIXFc with haemophilia A or haemophilia B in a real-world setting. The 18-month follow-up period is considered to be long enough to see changes and/or show medium/long-term stabilization of joint status. Patients treated on demand are not included in the study, as this would lead to a too high variability in the patient population.

Joint outcomes will be described over time and reported in a quantitative/objective manner with HEAD-US and HJHS scores. These assessments are not always fully incorporated in routine clinical practice and are therefore intended to be investigated in the low-interventional setting of this study. Both examinations have been chosen due to their complimentary features – HJHS is a clinical assessment focused on functionality and HEAD-US is a more sensitive US assessment with the ability to detect structural joint damage and synovitis earlier on in the joint deterioration.

This study will not have a control group. The reason for this is that it is not considered needed to be able to evaluate the primary objective of the study.

Patients excluded from participation in this study (section 6.3.2) will have been assessed as not being suitable for the study.

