8.3.3 Analysis related to primary objective

The primary objective is to evaluate the overall joint status as detected by US in haemophilia A and B patients treated with rFVIIIFc or rFIXFc prophylaxis over the 18-month study period.

The primary endpoint is change from baseline in total HEAD-US score up to month 18 (EOS) and will be based on both the FAS and PP set.

The primary endpoint, change from baseline, will be calculated from baseline (Visit 1) to month 18 (EOS). The change in HEAD-US score will also be calculated from baseline to month 6 and month 12. Mean change from baseline for the primary endpoint, will be estimated using a generalized linear mixed model for repeated measures, adjusted for clinically important covariates (for example, age, severity of haemophilia, type of haemophilia, presence of joint disease at inclusion, prophylactic regimen and dose intensity) as applicable. The estimated mean

Sobi

Eftrenonacog alfa/Alprolix® - Efmorocog alfa/Elocta®

Clinical Study No: Sobi.HAEM89-007

change from baseline in Total HEAD-US score will be presented with 95% confidence interval. In general, patients with events that could affect the interpretation of the Total HEAD-US score but not leading to discontinuation of treatment will be included in the primary analysis. Patients with events leading to discontinuation of treatment will be included in the primary analysis including all data collected up to discontinuation. To assess the robustness of these results, sensitivity analyses will be performed including one based on the PP analysis set. Further details will be specified in the SAP.

Examples of subgroups that will be created if applicable, to further explore the endpoint are age (6-<12, 12-<18, \geq 18 years), severity of haemophilia (mild/moderate/severe), type of haemophilia (A/B), presence of joint disease at inclusion (synovial hypertrophy and/or osteochondral changes), prophylactic regimen (primary/secondary/tertiary), dose intensity cross tabulated by change vs. no change in HEAD-US score, treatment (on demand vs. prophylaxis) prior to enrolment into the study and compliance (if e.g. 20% of the patients have < 80% compliance).

If there are few mild and moderate patients then these two severities will be pooled.

The HEAD-US score represents the sum of item scores for abnormalities detected. Its values range from 0 (minimum) to 8 (maximum), see Table 4.

Table 4 **HEAD-US scoring method**

Disease activity (synovitis)	Scale

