8.3.7 Interim analysis

Interim analyses are planned to be performed during the study. The first interim analysis is to be performed once recruitment is completed. The purpose of the first interim analysis is to assess the baseline variability of HEAD-US results and to share baseline characteristics with the haemophilia community. The second interim analysis is planned to be performed once at least 50% of the patients have completed their 12-month visit and will evaluate the joint health status at that time.

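### Does a half width below 2 fall short because the study may want to conclude that joints are stable?

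*Combined protocol and SAP*

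**What the plan says.** Protocol section 8.1 and the synopsis justify the sample size by the width of a confidence interval. With 250 patients (200 haemophilia A, 50 haemophilia B) and SD 13, the mean change "will be estimated with a level of accuracy that is lower than a clinically meaningful worsening of 2, e.g. a half width of 1.61". The SD is attributed to "expected variability among the patients with regards to prior treatment before enrolment and the diversity of joint status". Table 3 adds half widths for SD 7 and SD 10 at n=250, and for SD 13 at n=200.

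Section 8.3.3 makes a model-based estimate the main output: the mean "change from baseline in Total HEAD-US score will be presented with 95% confidence interval". Section 8.3.1 plans no hypothesis test. The primary objective (5.1) is to evaluate joint status, and the study rationale (4.2) is to describe joint health.

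Stability appears in two places. Section 4.1 says the outcome expected under adequate prophylaxis "is at least the maintenance of a stable joint status or the improvement in reversible lesions". Section 6.2 says that 18 months is "considered to be long enough to see changes and/or show medium/long-term stabilization of joint status".

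On variability, section 8.3.7 says: "The purpose of the first interim analysis is to assess the baseline variability of HEAD-US results". On its timing it says: "The first interim analysis is to be performed once recruitment is completed".

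**The concern.** Section 8.1 sets the half width beside a worsening that it calls clinically meaningful, and sections 4.1 and 6.2 have stable joints in view. A reader may therefore take the sizing to mean that, if joints are stable, the interval will exclude a worsening of 2. A half width below 2 does not secure that. It limits the distance from the estimate to the upper limit, while the estimate itself varies around the true value. At a half width of exactly 2, a cohort with zero true change has an upper limit above 2 half the time.

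If the SD of change is 13, roughly one study in three with truly stable joints would report an interval that still contains the plan's own meaningful worsening. The plan does not say how the interval will be read against 2 and gives no data source for the SD. Its only scheduled look at variability concerns baseline scores and comes when enrolment can no longer respond. The adequacy of 250 patients and the wording of the main conclusion would seem to be at stake.

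**Working it through.** **Inputs.** From section 8.1 and Table 3: SD 13 (also 10 and 7), n = 250 and 200, reference worsening 2. From section 8.3.3: 95% interval. The true mean change of zero is an assumption; the plan gives no number for it.

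**Step 1. Reproduce Table 3.** Half width = 1.96 × SD/√n.

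| SD | n | SE | Half width | Table 3 |
|---|---|---|---|---|
| 7 | 250 | 0.443 | 0.868 | 0.87 |
| 10 | 250 | 0.632 | 1.240 | 1.25 |
| 13 | 250 | 0.822 | 1.611 | 1.61 |
| 13 | 200 | 0.919 | 1.802 | 1.80 |

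All agree to about 0.01. The 1.25 matches the t quantile (1.246), whereas 1.61 and 1.80 match the normal quantile; this is immaterial.

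**Step 2. Chance that the upper 95% limit is below 2 at zero true change.** P = Φ(2/SE − 1.96). For SD 13, n=250: 2/0.822 = 2.43, and Φ(2.43 − 1.96) = Φ(0.47) = 0.68.

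| SD | n | Normal | Noncentral t |
|---|---|---|---|
| 13 | 250 | 0.682 | 0.678 |
| 13 | 200 | 0.585 | 0.581 |
| 10 | 250 | 0.885 | 0.883 |
| 10 | 200 | 0.807 | 0.804 |
| 7 | 250 | 0.995 | 0.994 |
| 7 | 200 | 0.981 | 0.980 |

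Simulation of 100,000 studies at SD 13 gave 0.678 (n=250) and 0.579 (n=200). At SD 13 the estimate must lie below 2 − 1.611 = 0.389 (n=250) or 2 − 1.802 = 0.198 (n=200). A half width of exactly 2 needs n = (1.96 × 13/2)² = 162.3 and gives Φ(0) = 0.50. With SD 13 and n=250, a true change of −0.5 gives 0.86 and of +0.5 gives 0.45.

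**Step 3. How firm is SD 13?** It is the largest of the three tabulated values. The reason given for it describes spread between patients, which is not the same as spread of within-patient change. Suppose 13 were the SD of scores at one visit (an assumption). The SD of change would then be 13 × √(2(1 − r)): 13 at r = 0.5, 10.1 at r = 0.7 and 8.2 at r = 0.8, giving chances of about 68%, 88% and 97% at n=250. Alternatively, keep 13 as the unadjusted SD of change and let the covariates in the 8.3.3 model explain 10%, 20% or 30% of the variance (assumed). The chance is then 73%, 78% or 83%. The documents cannot settle which case applies.

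**Step 4. What would the possible changes achieve?**

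- *More patients.* For an 80% chance at SD 13, n = ((1.96 + 0.842) × 13/2)² = 331.6, so 332, or 82 more than planned; 90% needs 444. Both percentages are conventional benchmarks, not figures in the plan. With 250 patients, 80% is reached at any SD up to 2 × √250/(1.96 + 0.842) = 11.3.
- *Checking the SD of 6-month change during recruitment.* Under section 6.1, "The recruitment period is planned to be approximately 12 months". With even accrual (assumed), about 250 × 3/12 ≈ 60 patients would have month-6 scans by month 9. An observed SD of 13 would have 95% limits of 13 × 0.848 = 11.0 and 13 × 1.220 = 15.9. That range contains 11.3, so the check could not decide between 250 and 332. It would also measure 6-month change, not 18-month change.
- *Printing the probability beside the half width.* This alters no analysis and no result.

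**The case for a change.** The strongest case for changing the plan is that the sponsor chose 2 as its own yardstick and expects stability. With no reading rule fixed in advance, an estimate of 0.7 at SD 13 and n=250 (interval 0.7 ± 1.61, so −0.91 to 2.31) could be written up as stable joints although it contains the meaningful worsening. The SD that decides whether 250 is tight or ample has no cited data behind it. Withdrawn patients are not replaced (6.3.4) and section 8.1 states no dropout allowance, so fewer than 250 may be evaluable at month 18, although the repeated-measures model keeps their earlier visits.

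Part of this stands. Precision below 2 and exclusion of 2 are different things, and anyone who later claims stability should know that. But the reading rule (upper limit below 2, otherwise not shown) is not one the plan adopts. It follows directly from a reported interval and a stated reference value, so analysts and readers can apply it without an amendment. Sections 8.3.1 and 8.3.3 leave further analysis detail to a SAP due before the first patient enters. Nor does the description of joint status rest on one interval limit: section 8.3.4 also covers the synovium, cartilage and bone scores, HJHS, and target joints.

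The n=200 figure needs care. Table 3 does not label that row, and 200 is also the planned number with haemophilia A, so 58% may describe that subgroup rather than a depleted whole study.

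**Conclusion.** No change follows. The stated half widths are right, and the plan meets the precision criterion that it sets. Sizing a single-arm descriptive study on interval width is a fair choice, and the 68% is not a shortfall against any stated power or margin. It rests on zero true change and on the largest SD in Table 3; at 250 patients the figure is about 88% at SD 10 and 99% at SD 7. Enrolling 332 patients would serve a target that the plan does not set, and a check on about 60 patients could not settle the SD. How the interval is read against 2, and the source of the SD, are details that the analysts can supply. The sponsor could usefully say whether it means to conclude stability, and otherwise keep the claim to estimation, but the analysis is sound without it.
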